### 4.3 Planned Duration of Study

The expected duration of participation for each participant who completes all study visits, from Screening to the EOS visit, is up to 16 weeks. The treatment duration for both Part A and Part B of the study are expected to be the same, as procedures are identical.

- Screening may take up to 28 days.

- The Baseline/Preparatory Period could last up to 4 days and should not be performed >4 days prior to Day 1.
- Enrollment confirmation will take place prior to dosing on Day 1; once enrollment has been confirmed, the Treatment Period will commence.
- The 4-week Treatment Period will consist of four dose sessions 1 week apart, with a telephone visit 1 day after each dose session for collection of safety assessments (AEs, concomitant medications, and C-SSRS) and a follow-up visit to assess safety and efficacy 2 days after each dose session.
- After the final session of the Treatment Period (Visit 14), participants will enter the Follow-Up period. Participants will attend a Follow-Up visit and a Reflection Session approximately 1, 2 and 3 weeks after the final study drug administration, followed by an EOS visit 6 weeks after the final study drug administration. Participants will also be contacted via telephone for collection of safety assessments on Day 57 ( $\pm 2$  days).
- Participants withdrawing before completion of the study should be encouraged to attend a visit that would duplicate the EOS visit to collect safety and efficacy information.

#### 4.4 Rationale for Study Design

This two-part study is designed to assess the safety and efficacy of four dose sessions of methylone over 4 weeks in participants with PTSD.

Part A will be an open-label, non-controlled assessment to confirm procedures to be used in Part B; with the exception of inclusion of a placebo-control in Part B, procedures will be identical. Double-blinding with use of placebo is included in Part B of the study to permit a true assessment of the safety and tolerability of methylone and to evaluate the benefits and risks of methylone. This design also allows for an objective assessment of key safety issues such as suicidality, which can be part of the disease process (PTSD) rather than a side effect of treatment.

Also included are standard assessments to evaluate the safety and tolerability, such as vital signs, physical examination, 12-lead ECGs, clinical laboratory evaluations and AE collection.

The battery of clinical outcome assessments to be performed are those routinely used to assess the severity of PTSD symptoms and functional impairment. These include observer-blinded assessments of PTSD severity and self-administered questionnaires that explore the participant's experience of life events. These questionnaires and scales are standardly used in clinical trials investigating psychoactive medications in similar patient populations.

#### 4.5 Dose Rationale

Both efficacy and safety are likely dose-related. [REDACTED]

[REDACTED] The relatively short half-life of methylone (translates to duration of effect) recommends the use of an initial dose (150 mg) followed by a booster (100 mg, within an individual dose session) to provide for a longer physiological impact, while reducing the  $C_{max}$  (compared with a single dose of 250 mg) which would provide for a safer dosing regimen.

In order to further enhance the likelihood of benefit, it is proposed that each participant should attend four dose sessions.

[REDACTED]

[REDACTED]

[REDACTED]

[REDACTED]

[REDACTED]

[REDACTED]

[REDACTED] The most common safety findings were increases in blood pressure and heart rate.

[REDACTED]

[REDACTED]

[REDACTED]

[REDACTED]

[REDACTED]

[REDACTED]

[REDACTED]

[REDACTED]

The methylone dose level has been selected as it is believed that this dose will maximize the opportunity to observe a clinical effect, but at the same time is anticipated to be well tolerated. To that end, administering methylone over four dose sessions at weekly intervals has been selected. At each dose session, there will be an initial administration of 150 mg followed by a booster administration of 100 mg after 90 minutes ( $\pm 10$  minutes).

- Based on the completed Phase 1 studies and PK modelling, an initial administration of 150 mg would be anticipated to induce meaningful psychological effects that would be extended by the booster administration of 100 mg given 90 minutes later ( $\pm 10$  minutes).
- Based on the retrospective case series, the use of multiple dose sessions would optimize the likelihood of a clinical benefit.
- This dose regimen would provide a total dose during a dose session of 250 mg, but because the dose is split, the  $C_{max}$  is anticipated to be lower than if 250 mg was given as a single dose.
  - This initial administration is lower than the maximum single dose given to the healthy volunteers (up to 300 mg) in the open-label Phase 1 study.
  - The proposed dose is significantly lower than the dose given to most patients reported in the Case Series.

Taken together, these data suggest that a dose of 150 mg plus a booster dose of 100 mg administered on four occasions over 4 weeks would provide a physiological response that is believed to predict clinical benefit, and that this regimen would be well tolerated and provide confidence that this proposed study can be conducted safely.

To further ensure the safety of participants, all study drug administration will be under the direct supervision of the Research Site Staff and a dosing session monitor, and a DSMB will regularly review emerging safety data.

## **4.6 End of Study**

### **4.6.1 End-of-Study Definition**

The EOS is defined as the date of the last visit of the last participant in the study.

A participant is considered to have completed the study if the participant has completed all periods of the study including the last visit (Day 64).

### **4.6.2 Exit Plan**

At the conclusion of each participant's participation, they will be provided with an Exit Plan. The Exit Plan summarizes the study treatment, their current medications, and provides them a contact for more information about the study if needed. Participants may request a referral for further therapeutic or medical care if appropriate. Enrolled participants who terminate the study early will be provided an Exit Plan at their last contact. Participants who continue into an extension study are not required to have an Exit Plan.

## **4.7 Data and Safety Monitoring Board**

The objective of the DSMB is to review safety data (Part A and Part B) during the clinical trial.

The DSMB will comprise:

- A psychiatrist, preferably with PTSD experience.
- Cardiologist/Internal medicine specialist.
- A statistician.

Data and Safety Monitoring Board meetings will be scheduled to occur after 8 participants in Part A have completed the Day 29 Follow-Up visit, or EOS if the participant withdraws early

(Safety Run-in Phase) and once after all participants in Part A have the opportunity to complete the Day 29 Follow-Up visit.

For Part B, DSMB meetings will occur at intervals of approximately 20 participants completing the Day 29 Follow Up Visit or EOS if the participant withdraws early. Ad hoc DSMB meetings will occur as needed.

The safety and tolerability data to be reviewed will include, at a minimum, AEs, physical examinations, 12-lead ECGs, vital signs, clinical laboratory evaluation results, and C-SSRS results, summarized by a non-voting Statistician. There are no stopping rules for either efficacy or futility.

Further details on the operation of the DSMB will be defined in a standalone supporting document.

#### **4.8 Criteria For Termination of Dosing for An Individual Participant**

Dosing will be terminated for an individual participant if **any** of the following occur:

- 1) If a participant experiences an intolerable AE.
- 2) If a participant demonstrates significant non-compliance.
- 3) If a participant is administered a prohibited medication which, in the opinion of the Investigator and Medical Monitor, has the potential to significantly impact participant safety or data integrity.
- 4) If a female participant becomes pregnant.
- 5) If any participant reports Active Suicidal Ideation since last study drug administration, as evidenced by a 'Yes' response to the C-SSRS Suicidal Ideation questions 4 or 5.
- 6) If a participant reports any suicidal behavior since last study drug administration, as evidenced by a 'Yes' response to the following suicidal behavior questions on the C-SSRS:
  - a) Actual attempt, or
  - b) Interrupted attempt, or
  - c) Aborted attempt.
- 7) If a participant experiences Grade 3 Hypertension (as defined in the National Cancer Institute CTCAE [Version 5.0]) during a dosing session:
  - a) Grade 3: SBP  $\geq$ 160 mmHg or DBP  $\geq$ 100 mmHg, requiring the need for medical intervention with more than one drug or more intensive therapy than previously used.
- 8) If a participant develops an abnormality of liver function tests (LFTs) that meets the following criteria during the treatment period:
  - a) Aspartate aminotransferase (AST) or alanine aminotransferase (ALT):
    - i)  $>$ 5-fold upper limit of normal (ULN), or
    - ii)  $>$ 3-fold ULN with concomitant serum total bilirubin  $\geq$ 2-fold the ULN with  $\geq$ 35% direct.
- 9) If a participant experiences a clinically significant elevation of their temperature by  $>$ 2.0°C (and  $\geq$ 38°C) during the dosing session.

- 10) If a participant experiences a severe psychological event related to dosing that requires an intervention.
- 11) If a participant experiences a cardiovascular event associated with dosing that requires an intervention.
- 12) If a participant develops a neurological deficit.
- 13) If a participant experiences a treatment-related SAE.
  - a) Note that an SAE that is considered not treatment-related by the Investigator should not automatically lead to discontinuation of dosing. Instead, that participant and the SAE should be discussed with the Medical Monitor and Sponsor (or delegate) to make a determination as to whether dosing should continue or be terminated.

Any participant who discontinues the study early will complete an Early Termination visit and an Exit Plan will be provided to the participant.

#### 4.9 Criteria for Interruption of Randomization/Dosing of New Participants

If the following occur, enrollment/randomization and dosing of new participants will be interrupted until a DSMB review has indicated that it is safe to continue:

- 1) If there appears to be an unacceptable tolerability profile based on the nature, frequency and severity of observed AEs and/or clinical safety monitoring.
- 2) If **two** participants report Active Suicidal Ideation since last study drug administration, as evidenced by a 'Yes' response to the C-SSRS Suicidal Ideation questions 4 or 5.
- 3) If **two** participants report any suicidal behavior since last study drug administration, as evidence by a 'Yes' response to the following suicidal behavior questions on the C-SSRS:
  - a) Actual attempt, or
  - b) Interrupted attempt, or
  - c) Aborted attempt.
- 4) If **two** participants experience Grade 3 Hypertension (SBP  $\geq$ 160 mmHg or DBP  $\geq$ 100 mmHg), or Grade 2 (SBP  $\geq$ 140 mmHg or DBP  $\geq$ 90 mmHg), (as defined in the National Cancer Institute CTCAE [Version 5.0]), persisting over 48 hours post dosing, and require the need for medical intervention with more than one drug or more intensive therapy than previously used.
- 5) If **two** participants develop an abnormality of LFTs that meets the following criteria during the treatment period:
  - a) AST or ALT:
    - i)  $>$ 5-fold ULN, or
    - ii)  $>$ 3-fold ULN with concomitant serum total bilirubin  $\geq$ 2-fold the ULN with  $\geq$ 35% direct.
- 6) If **two** participants experience a clinically significant elevation of their temperature by  $>$ 2°C (and  $\geq$ 38°C) during the dosing session.
- 7) If **two** participants experience a severe psychological event related to dosing that requires an intervention.

- 8) If **two** participants experience a cardiovascular event associated with dosing that requires an intervention.
- 9) If **two** participants develop a neurological deficit.
- 10) If **three** participants experience a treatment-related SAE of any nature.
- 11) If **two** participants experience the same SAE.

The Investigators and Sponsor have the right to terminate the study or suspend enrollment at any time. The Investigator(s) will be notified by telephone and in writing if the Sponsor decides to suspend or terminate the study for any reason. The written notice will provide the Investigator with the reason that the site and/or study was suspended or terminated, along with instructions on how the site should proceed. Should the Sponsor terminate the study early, all participants will complete an Early Termination visit and an Exit Plan will be provided to the participant.

Reasons for terminating the study may include, but are not limited to, the following:

- Discovery (from this or other studies) of an unexpected, serious or unacceptable health hazard to participants.
- A decision on the part of the Sponsor to suspend or discontinue testing, evaluation or development of the product.
- Evidence from the data that there are sufficient technical problems with the study to believe with a high degree of certainty that participants are being exposed without a realistic expectation of evaluable data.
- Participant enrollment is unsatisfactory.
- Insufficient adherence to Protocol requirements or an unacceptably high rate of missing, erroneous or improperly collected data that threaten the scientific integrity of the study.

Reasons for suspending enrollment at a site may include, but are not limited to, the following:

- Failure of the Investigator to comply with pertinent regulatory regulations.
- Submission of knowingly false information from the research facility to the Sponsor.
- Participant enrollment is unsatisfactory.
- Insufficient adherence to Protocol requirements or an unacceptable high rate of missing, erroneous or improperly collected data that threaten the scientific integrity of the study.

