### 7.6 Columbia-Suicide Severity Rating Scale

The C-SSRS will be used to assess suicide potential or tendency as a study entry criterion and monitored throughout the study.

The C-SSRS is a semi-structured interview designed to assess the severity and intensity of suicidal ideation, suicidal behavior and non-suicidal self-injurious behavior over a specified time period. The measurement of suicidal ideation is based on five 'yes' or 'no' questions with accompanying descriptions arranged in order of increasing severity. If the participant answers 'yes' to either questions 1 or 2, the intensity of ideation is assessed in five additional questions related to frequency, duration, controllability, deterrents and reasons for the most severe suicidal ideation. Suicidal behavior is assessed by asking questions categorizing behaviors into actual, aborted and interrupted attempts; preparatory behavior, and non-suicidal self-injurious behavior.

If any item(s) on the C-SSRS are answered ‘yes’, the Investigator must review the participant’s responses in order to (a) at the Screening visit and Baseline/Preparatory session to determine the participant’s study eligibility and potential need for referral to a mental health professional, and (b) during the study evaluate the participant’s need for appropriate medical management such as a referral to a mental health professional, or appropriateness of further study drug administration in consultation with the Medical Monitor and Sponsor.

A significant risk of suicide is defined as a ‘yes’ in answer to:

- (a) questions 4 or 5 on the suicidal ideation section; or,
- (b) any questions on any item in the suicidal behavior section.

This must be reported as an AE or SAE as appropriate and followed up accordingly. Additionally, if a participant responds ‘yes’ to any of the suicidal ideation questions 1 through 3, the Investigator should apply clinical judgement to determine the need for reporting this as an AE or SAE and the need for any appropriate referral.

For any participant who responds ‘yes’ to relevant questions post-study drug administration, they will be handled appropriately.

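### Protocol 4.9 item 3 leaves completed suicide out of its two-participant count, so one suicide plus one attempt does not force the pause that two attempts force

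*Protocol*

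**What the plan says.** Section 4.9 of the protocol lists events that stop enrollment, randomization and dosing of new participants until the DSMB finds it safe to go on. The items that bear on suicidality are these:

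- Item 1, with no count: "If there appears to be an unacceptable tolerability profile based on the nature, frequency and severity of observed AEs", or on clinical safety monitoring.
- Item 2: two "participants report Active Suicidal Ideation since last study drug administration", meaning a positive answer to C-SSRS ideation question 4 or 5.
- Item 3, with a threshold of two people: "participants report any suicidal behavior since last study drug administration, as evidence by a 'Yes' response to the following suicidal behavior questions on the C-SSRS". Three questions follow: actual, interrupted and aborted attempt.
- Item 7: two "participants experience a severe psychological event related to dosing that requires an intervention".
- Item 10: three "participants experience a treatment-related SAE of any nature".
- Item 11: two "participants experience the same SAE".

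The same three-question list appears in section 4.8, item 6, which ends dosing for an individual: "If a participant reports any suicidal behavior since last study drug administration". Leaving out completed suicide does no harm there, because no further dose could be given.

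SAP 6.2.6 describes ten yes/no C-SSRS categories. Category 9 is an actual attempt, marked as non-fatal; Category 10 is completed suicide. The SAP counts Categories 6 to 10 as suicidal behavior. Protocol 7.7.1.3 also names suicides and suicide attempts separately among the adverse events of special interest (AESIs).

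**The concern.** Item 3 is the counted trigger for suicidal behavior, and its list omits the most serious outcome in that domain. A participant who dies by suicide adds nothing to the count. Two aborted attempts therefore force a pause, while a death plus an attempt is left to discretion.

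The protocol treats suicidality as a key safety issue (4.4), describes ideation and attempts as known complications of PTSD, and administers the C-SSRS at every contact (5.6.3). It gave suicidality its own counted triggers in addition to the judgement-based item 1, so that a pause need not wait for someone to assess overall tolerability. Scheduled Part B DSMB meetings come only after about every 20 participants reach Day 29 or leave early (4.7). Without a trigger or a discretionary decision, new participants could be dosed before the next review.

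**Working it through.** No event rate or sample-size figure is needed; this is a check of a counting rule.

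**Inputs.** Item 3: threshold 2, qualifying events actual, interrupted or aborted attempt. Item 10: threshold 3, treatment-related SAEs. Item 11: threshold 2, same SAE. All are from protocol 4.9. The separation of non-fatal attempt from completed suicide is from SAP 6.2.6.

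**Notation.** Let s be the number of participants with a completed suicide, and a the number of other participants with a positive answer to one of the three listed questions. With s + a equal to 1 or 2 there are five cases.

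**Formulas.**

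- Item 3 as worded: count = a, pause at 2.
- Item 3 with completed suicide added: count = s + a, pause at 2.
- Item 11, narrow reading (a suicide and an attempt are different SAEs): count for suicides = s, pause at 2.
- Item 10: count from these events is at most s + a ≤ 2, below 3.

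**The plan's own figure.** With s = 0 and a = 2, item 3 counts 2 and pauses. Every pairing of the three listed attempt types gives the same result, which reproduces the stated two-participant threshold.

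| Case | s | a | Item 3 now | Counted pause now | Item 3 after change | Pause after change |
|---|---|---|---|---|---|---|
| One attempt | 0 | 1 | 1 | No | 1 | No |
| One suicide | 1 | 0 | 0 | No | 1 | No |
| Two attempts | 0 | 2 | 2 | Yes, item 3 | 2 | Yes |
| Two suicides | 2 | 0 | 0 | Yes, item 11 (count 2) | 2 | Yes |
| One suicide, one attempt | 1 | 1 | 1 | No (narrow reading of item 11) | 2 | Yes |

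One case of five changes: the last.

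**Do the other items catch that case?**

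- Item 11 stands at 1 of 2. It reaches 2 only if both events are SAEs and are read as the same SAE. Section 4.9 does not define that term, and the attempt may not be an SAE at all. For a positive behavior answer, section 7.6 says: "This must be reported as an AE or SAE as appropriate and followed up accordingly".
- Item 10 stands at no more than 2 of 3 from these two events.
- Item 2 is met only if both participants had also reported ideation 4 or 5.
- Item 7 is met only if both events are judged severe, related to dosing and needing intervention.
- No item in 4.9 is triggered by a death or by an AESI as such.

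**The case against.** The strongest reply has four parts.

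**The gap depends on reading the SAP into the protocol.** The protocol's own C-SSRS description (7.6) puts no non-fatal qualifier on an actual attempt, and item 3 opens by speaking of any suicidal behavior. A reader could treat a suicide as a fatal actual attempt. That reading is possible but strained: item 3 requires a participant to report the behavior and answer a question, and 7.7.1.3 names suicides and attempts separately. If it is the intended reading, the added line only confirms it.

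**Item 1 is mandatory and fits.** Once the profile is judged unacceptable, the pause must follow, and a suicide plus an attempt is the kind of evidence it has in view. Items 7, 8 and 10 also involve judgement. This stands, and it means the trial does have a route to pause. But item 1 begins with an assessment, whereas two attempts force the pause with none.

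**Item 11 may apply.** An attempt can meet SAE criteria, and 7.7.1.3 groups suicides and attempts under one heading. A safety rule should not turn on how an undefined term is read.

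**The practical effect is small.** Exclusions 8 and 9 remove participants with recent ideation 4 or 5 or with suicidal behavior in the last 5 years. Suicide-risk AESIs reach the sponsor within 24 hours, ad hoc DSMB meetings are available, and the sponsor and investigators may suspend at any time. Section 4.9 stops only new participants, so the change does nothing once enrollment has ended. All of this stands. It limits the importance of the point but does not remove the inconsistency.

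It is also fair that one case in five is a count of combinations, not a probability. Other SAEs already accrued, or concurrent ideation, could bring item 10 or item 2 into play.

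**Conclusion.** The point holds. On the wording of item 3, one suicide plus one attempt counts 1 of 2, and no other counted item reliably makes up the difference. The more serious pair of events therefore gets a weaker mandatory response than two non-fatal attempts.

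The conclusion rests on two readings: that actual attempt in item 3 means a non-fatal one, as in the SAP, and that a suicide and an attempt are not the same SAE under item 11. If either reading is rejected, the mixed pair could already pause; on the second, only if the attempt is itself an SAE.

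This does not show that the trial could not pause after such events, or that they are likely. A single suicide would still fall short of item 3's count after the change, as any single event does. It is a low-cost correction to a stated safety rule and worth making.

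**What to change.** In protocol 4.9, item 3, add completed suicide after the first dose, counted from any source of report, toward the existing two-participant trigger, with each participant counted once. The wider source of report is needed because someone who has died cannot answer the C-SSRS. The time window is in effect unchanged, since any suicide after the first dose falls after that participant's last dose. Leave every other threshold in 4.9 as it is.

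The cost is one line of text, with no added visits, data collection or sample size. The downside is an occasional pause, ended by DSMB review, for an event that proves unrelated to treatment.
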